16.1.5.2 Demographic and baseline characteristics

Demographic and baseline characteristics (eg physical examination, vital signs and ECGs) will be summarised.

Subjects who take concomitant medication will be listed.

16.1.5.3 Treatment compliance

Dates and times of dosing will be listed.

16.1.6 Safety data analyses

Summaries and listings of safety data will use the safety population.

16.1.6.1 Adverse events

AEs will be coded using the version of the Medical Dictionary for Regulatory Activities (MedDRA) current at the time of database lock.

All AEs will be listed.

A treatment-emergent adverse event is an AE that emerges during treatment (having been absent before treatment) or that worsens after treatment¹².

The number of subjects with at least one TEAE will be tabulated by actual treatment and MedDRA system organ class and preferred term.

For each of the following, the number of TEAEs and the number of subjects with TEAEs will be summarised by actual treatment as follows:

- TEAEs, by system organ class and preferred term
- TEAEs by system organ class, preferred term and severity
- drug-related TEAEs, by system organ class and preferred term

Subjects with more than one TEAE will be counted only once, at the maximum causality, for each system organ class and preferred term. AEs with missing severity and/or causality will be treated as severe and possibly related, respectively.

AEs leading to withdrawal, deaths and other SAEs will be listed separately (fatal events will be listed separately from non-fatal events).

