2.3 Endpoints

2.3.1 Primary endpoints

Safety and tolerability:

Clinically significant changes in: vital signs (heart rate, blood pressure, respiratory rate, pulse oximetry, and temperature), 12-lead electrocardiogram (ECG), forced expiratory volume (FEV₁), forced vital capacity (FVC), physical examination, nasal examination, laboratory safety tests (haematology, biochemistry and urinalysis), tolerability questionnaire, number and severity of adverse events (AEs) and serious AEs. Safety endpoints will be assessed up to 7 days after dosing in Part A or up to 14 days after the last dose in Part B.

2.3.2 *Exploratory endpoint*

PD: SARS-CoV-2 infection test, done at screening, before the first dose, on Day 8 (Part B only), and at follow-up.

Immunogenicity: ADAs of Neumifil, as assessed by immunoglobulin A and G (IgA and IgG) concentration, derived from blood samples taken before the first dose and at follow-up (Part B only).

Plasma concentrations of Neumifil: Plasma concentrations of Neumifil after single doses on Day 1 in Part A, and after dosing on Days 1 and 7 in Part B.

Cytokine and chemokine concentrations in nasal secretions: Presence and concentration of cytokines and chemokines, measured by multiplex assay, in nasal wick samples collected on Day –1, Day 8, and at follow up (Part B only).

2.4 *Type of trial*

This is a Phase 1, single-centre, randomised, placebo-controlled first-time-in-human (FTIH) study in healthy subjects. The study is in 2 parts and will investigate single-ascending (Part A) and multiple-ascending (Part B) doses of Neumifil, administered intranasally.

2.5 *Trial design and methods*

2.5.1 *Part A*

Part A is a randomised, double-blind, placebo-controlled, single ascending dose study. Enrolment of up to 36 healthy subjects is planned, in up to 5 groups (Groups A1–A5). Groups A1–A3 will consist of 6 subjects each and Groups A4 and A5 will consist of 9 subjects each.

Subjects will receive a single intranasal dose of Neumifil or placebo. In Groups A1–A3, 4 subjects will receive Neumifil and 2 will receive matching placebo. In Groups A4 and A5, 6 subjects will receive Neumifil and 3 will receive matching placebo.

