An event for which, after careful medical evaluation, a connection with trial medication cannot be ruled out with certainty. The event occurs after exposure to trial medication. The event may occur at a reasonable time in relation to the time of administration of the trial medication but might also be attributable to a commonly occurring alternative cause. Alternatively, the event may not occur at a reasonable time in relation to the time of administration of trial medication but may not be attributable to an alternative cause.

Not related

An event which occurs before exposure to the trial medication, or which does not occur at a reasonable time in relation to the time of administration of trial medication and can be attributed to a commonly occurring alternative cause. Alternatively, the event is unrelated to the trial (eg road traffic accident), unless it can be demonstrated that the treatment could have caused the event.

- **Action taken:** none, drug treatment, subject withdrawn, other (specified).
- **Outcome:** recovered/resolved, recovering/resolving (or not recovered/not resolved), or unknown.

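### The only subject-counting rule for TEAEs selects on causality, so the table by severity has no defined grade for some subjects and too low a grade for others

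*Combined protocol and SAP*

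**What the plan says.** Section 16.1.6.1 states that "the number of TEAEs and the number of subjects with TEAEs will be summarised by actual treatment", and lists three tables: all TEAEs by system organ class (SOC) and preferred term (PT); "TEAEs by system organ class, preferred term and severity"; and "drug-related TEAEs, by system organ class and preferred term".

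One rule for subjects with several events follows the list and is not limited to any one table: "Subjects with more than one TEAE will be counted only once, at the maximum causality, for each system organ class and preferred term". The next sentence deals with missing values: "AEs with missing severity and/or causality will be treated as severe and possibly related, respectively".

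Section 14.2 defines three severity grades (mild, moderate, severe) and two causality categories. The definition of Related opens "An event for which, after careful medical evaluation, a connection with trial medication cannot be ruled out with certainty"; that of Not related opens "An event which occurs before exposure to the trial medication, or which does not occur at a reasonable time".

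The synopsis (section 2.3.1) includes in the primary endpoint the "number and severity of adverse events (AEs) and serious AEs". Section 7.2.1 lists AEs and SAEs but mentions neither number nor severity.

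Neither section 16.1.6.1, nor the general considerations in section 16.1.4, nor any other section says that a subject is counted at the worst severity.

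**The concern.** The severity table is the only one of the three in which choosing among a subject's events changes the row where the subject is counted. The first table has no split by severity or causality. In the drug-related table, with two causality categories, maximum causality means only that a subject is counted if any event is Related. The written rule therefore does no harm where the choice has no effect, and it fails in the one table that needs a choice.

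Two failures follow in that table:

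- **Undefined grade.** Two events with the same causality and different severities both sit at maximum causality, and nothing says which grade is counted. Two programmers could follow the text and produce different tables.
- **Grade too low.** A subject with a mild Related event and a severe Not-related event under one PT is counted as mild. The same table would then show one severe event and no subject with a severe event. This also applies when the Not-related event is severe only because its severity was missing. The cautious default for missing severity is then lost from the subject count.

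The trial is descriptive and tests no hypotheses (section 16.1.2), so tables such as this one carry the safety results.

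**Working it through.** The documents give no figure on this point, so there is none to reproduce. The check applies the written rule to every possible pair of events that one subject can have under one PT.

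**Inputs**

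- Severity: 3 grades (section 14.2).
- Causality: 2 categories (section 14.2).
- Rule: take the event or events at maximum causality; the counted grade is theirs (section 16.1.6.1).
- Active subjects per group: 4 in A1–A3 and 6 in A4–A5 (section 8.1.1); 6 in B1–B3 (section 8.1.2).

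**Enumeration**

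Event types: 3 × 2 = 6. Ordered pairs: 6 × 6 = 36.

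- *Same causality:* 2 × (3 × 3) = 18. In 2 × 3 = 6 the grades are equal, so the grade is defined. In 18 − 6 = 12 they differ, so it is undefined.
- *Different causality:* 2 orders × (3 × 3) = 18. In each order the Related event has the same grade in 3 pairs, the higher grade in 3 and the lower grade in 3. The rule gives the worst grade in 2 × (3 + 3) = 12 and too low a grade in 2 × 3 = 6.
- *Severe event displaced:* mild Related with severe Not related, and moderate Related with severe Not related, in 2 orders: 2 × 2 = 4 of the 6.

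A choice is needed only when the grades differ. Equal grades account for 6 + 6 = 12 ordered pairs, which leaves 36 − 12 = 24.

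| Patterns | Total | Worst grade | Undefined | Too low |
|---|---|---|---|---|
| Ordered, all | 36 | 6 + 12 = 18 | 12 | 6 |
| Ordered, grades differ | 24 | 18 − 12 = 6 | 12 | 6 |
| Unordered, all | 21 | 12 | 6 | 3 |
| Unordered, grades differ | 12 | 3 | 6 | 3 |

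The rule ignores the order of events, so the unordered rows are the more natural summary. The three unordered patterns that come out too low are mild Related with moderate Not related, mild Related with severe Not related, and moderate Related with severe Not related.

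**Other readings of the text**

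- *The rule covers only the drug-related table.* The severity table then has no grade rule, and all 24 ordered patterns with differing grades are undefined.
- *A subject is counted once at each severity level.* This conflicts with counting once per SOC and PT.
- *The missing-value sentence supplies the rule.* It fills in single missing values and does not choose among several events.

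**Weight of one subject:** 1/4 = 25% in A1–A3; 1/6 = 16.7% in A4–A5 and B1–B3.

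**With maximum severity as the rule:** all 21 unordered patterns give one defined grade, and it is the worst grade.

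**The case against.** The strongest reply is that the causality sentence follows directly after the drug-related table and fits it naturally. Read that way, nothing is understated and the protocol merely omits a grade rule, which the SAP scheduled in section 16.1.1 could supply. It is fair that the too-low result depends on applying the sentence to all three tables. But the sentence is not restricted, and the narrower reading leaves the severity table with no rule at all. The SAP text is not in the documents, and nothing in section 16 signals that a correction is needed.

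A second reply is that the too-low pattern should be uncommon. Related is defined broadly, so two events under one PT in one subject will usually share a category. That stands, but it makes the causality tie, which is the undefined case, the more likely failure.

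Third, repeat events may be few. Section 14.2 makes any questionnaire score above 0 an AE, and Part B has questionnaires at two times after each of seven once-daily doses (2 × 7 = 14; section 12.1.2). The protocol does not say that each score is a separate AE, and it has a field for intermittent events. The frequency is therefore unknown, and the 25% figure belongs to single-dose groups, where repeats are least expected.

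Finally, all AEs are listed and event counts by severity are shown, so a reader can rebuild any cell. This limits the harm but does not make the planned subject counts reproducible from the plan.

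**Conclusion.** The concern holds. Section 16.1.6.1 states one counting rule that is unsuitable for the severity table, and no other section supplies a suitable one. Where a subject's two events differ in grade, the rule gives the worst grade in a quarter of the logical patterns (6 of 24), no defined grade in half (12 of 24) and too low a grade in a quarter (6 of 24). The narrower reading leaves all 24 undefined. These proportions weight every pattern equally and are not rates.

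The effect is confined to the subject counts in one descriptive table, where one misplaced subject is 25% or 17% of an active group. Event counts, the other two tables, the AE listing, review by the Safety Review Group (section 8.5.1) and the stopping rules (section 8.4) are unaffected. The conclusion rests on the two-category causality scale and three-grade severity scale of section 14.2, and on the absence of any other counting rule in the text supplied. It should be corrected, because severity is part of the synopsis primary endpoint and the correction is trivial.

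**What to change.** Replace the counting sentence in section 16.1.6.1 with: *In every table a subject is counted once per system organ class and preferred term. In the table by severity, the subject is counted at the maximum severity. In the drug-related table, the subject is counted if any event is Related.*

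The missing-value sentence stays and is applied before counting. As an optional tidy-up that changes no count, name the default for missing causality Related, since that is the category section 14.2 defines.

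The cost is one sentence, either in the protocol or in the SAP due before first database lock. It needs no new data and no change to any other section, and it leaves the counts in the other two tables as they are.

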16.1.6.2 Clinical laboratory evaluations

Data from haematology and clinical chemistry will be summarised by treatment.

Any laboratory value outside the reference interval for that variable will be flagged with an 'H' if it is higher than the reference interval, and with an 'L' if it is lower. Additionally, if, during the course of the trial, a variable changes from baseline by more than a predetermined amount (as defined by the principal investigator), that value will receive a flag 'I' if increased, or 'D' if decreased. Therefore, if a value both falls outside the reference interval and alters from the baseline value by more than the predetermined amount, it will attract a double flag and will be considered to be of potential clinical importance (PCI).

All laboratory values of PCI will be listed. In a separate listing, laboratory values of PCI will be listed with all related laboratory results (ie haematology or clinical chemistry). Frequencies of laboratory values of PCI will be summarised.

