9.3 Exclusion criteria

1. Woman who is pregnant or lactating, or pre-menopausal woman who is sexually active and not using a reliable method of contraception (see section 11).
2. Clinically relevant abnormal medical history, physical findings, ECG, or laboratory values at the pre-trial screening assessment that in the opinion of the

investigator could interfere with the objectives of the trial or the safety of the volunteer.

3. Presence or history of acute or chronic illness sufficient to invalidate the volunteer's participation in the trial or make it unnecessarily hazardous.
4. Presence or history of respiratory disease, including (but not limited to) asthma, chronic obstructive pulmonary disease (COPD), cystic fibrosis, emphysema, requiring acute or chronic medication.
5. Presence of nasal polyps or significant nasal abnormalities.
6. Symptoms of respiratory illness (including, but not limited to, runny nose, sore throat, sneezing, coughing or wheezing) at the screening visit or before dosing on Day 1.
7. Tympanic temperature $> 37.5^{\circ}\text{C}$ at the screening visit or before dosing on Day 1.
8. Impaired endocrine, thyroid, hepatic, respiratory or renal function, diabetes mellitus, coronary heart disease, or history of any psychotic mental illness.
9. History of psychiatric disease, as determine by the investigator.
10. History or presence of malignant disease.
11. Immune-suppressed status, resulting from either disease or medication, as determined by the investigator.
12. Presence or history of severe adverse reaction to any drug or the excipients of Neumifil.
13. Known allergy to tetracycline antibiotics.
14. Use of a prescription medicine (except HRT in female subjects), including oral contraceptives, during the 28 days before the first dose of trial medication, or use of an over-the-counter medicine, with the exception of acetaminophen (paracetamol) and vitamin or nutritional supplements, during the 7 days before the first dose of trial medication.
15. Receipt of an investigational product (including prescription medicines) as part of another clinical trial within the 3 months before admission to this study; in the follow-up period of another clinical trial at the time of screening for this study.
16. Receipt of a COVID-19 vaccine within 7 days before the first dose of trial medication, or anticipate receiving a COVID-19 vaccine within the 7 days after a (final) dose of trial medication.

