16.1.4 General considerations for data analyses

The minimum set of summary statistics for numeric variables will be: n, mean, standard deviation (or standard error), median, minimum, and maximum. 95% confidence intervals will be presented where appropriate for data interpretation.

Categorical data will be summarised in frequency tables with n and percentage. Summaries of a categorical variable will include all recorded values.

The minimum and maximum values will be presented to the same number of decimal places as the raw data collected in the CRF (or to 3 significant figures for derived parameters). The mean, median and percentiles (eg Q1, and Q3) will be presented to one additional decimal place. The standard deviation and standard error will be presented to 2 additional decimal places.

'Baseline' will be the latest value obtained before IMP administration (predose on Day 1, or Day -1 if not recorded at predose, or screening if not recorded at predose or on Day -1 [eg weight]). Out-of-range laboratory tests may be repeated. If a test is out of-range at baseline and repeated before dosing, the latest repeat value before dosing will be used as baseline. However, if a test is out-of-range and repeated at any other time during the study, the out-of-range value (not the repeat value) will be included in statistical summaries.

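### The laboratory PCI frequency pools values moving back towards normal with values getting worse, because the double-flag rule ignores direction

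*Combined protocol and SAP*

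**What the plan says.** Section 16.1.6.2 applies two independent flags to each laboratory value. A value outside the reference interval is "flagged with an 'H' if it is higher than the reference interval, and with an 'L' if it is lower". If a variable changes from baseline by more than an amount predetermined by the principal investigator, "that value will receive a flag 'I' if increased, or 'D' if decreased". A value is then PCI "if a value both falls outside the reference interval and alters from the baseline value by more than the predetermined amount". PCI values are listed, listed again alongside the related laboratory results, and counted: "Frequencies of laboratory values of PCI will be summarised".

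Nothing in 16.1.6.2 requires H to go with I, or L with D, and no other section adds a direction condition for laboratory values.

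Out-of-range baselines are foreseen. Section 16.1.4 says: "If a test is out of-range at baseline and repeated before dosing, the latest repeat value before dosing will be used as baseline". Exclusion criterion 2 in section 9.3 covers "laboratory values at the pre-trial screening assessment" only where the abnormality is clinically relevant and, in the investigator's opinion, could interfere with the trial's objectives or the volunteer's safety. Minor deviations can therefore enter.

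**The concern.** Four flag pairs qualify as PCI: H with I, L with D, H with D, and L with I. The first two are the pattern a safety table is meant to pick up. The last two are partial recovery from an abnormal baseline. A frequency that adds all four together does not tell the reader how much of it is deterioration.

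This also differs from the neighbouring rules. A treatment-emergent adverse event must be new or have worsened (section 16.1.6.1), and a QTcF change counts as PCI only if it is an increase (section 16.1.6.3). The groups are small: 4 or 6 active subjects per group in Part A and 6 in Part B. A few recovering values could therefore blur a comparison between dose levels in that table.

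**Working it through.** The plan states no figure for this, so there is none to reproduce. The check has three steps.

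**1. What the rule admits.** Let U and L be the reference limits, b the baseline, v the later value and d the predetermined amount.

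- H with D: v > U and b − v > d, so b > U + d. The distance above the interval falls from b − U to v − U, a reduction of more than d.
- L with I: v < L and v − b > d, so b < L − d. This is the mirror image.

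Both pairs are therefore always nearer the reference interval than baseline. A grid of baseline and later values, with d = 0.5, 1.0 and 1.5 SD, gave no exception.

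**2. How many baselines could lead to it.** Section 12.4, Table 7 lists 13 haematology and 20 biochemistry variables, 33 in all. With the 60 planned subjects there are 33 × 60 = 1,980 baselines. The following are assumptions, not taken from the documents: normal values, a 95% reference interval (limits at ±1.96 SD), d between 0.5 and 1.5 SD, and no eligibility screening. The baseline must lie beyond 1.96 + d:

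| d (SD) | Baseline beyond | Two-sided probability | Expected of 1,980 |
|---|---|---|---|
| 0.5 | 2.46 SD | 0.0139 | about 28 |
| 1.0 | 2.96 SD | 0.0031 | about 6 |
| 1.5 | 3.46 SD | 0.0005 | about 1 |

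These are candidates only. The later value must also fall by more than d (or rise, for a low baseline) and still be outside on the same side.

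**3. Share of double flags.** This is a simulation of 4 million baseline and later pairs per scenario, with no drug effect, the assumptions of step 2, and an assumed within-subject correlation of 0.5 to 0.85:

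| Correlation | d (SD) | All PCI per 1,000 results | H–D or L–I per 1,000 | Share |
|---|---|---|---|---|
| 0.50 | 0.5 | 40.29 | 1.468 | 3.6% |
| 0.50 | 1.0 | 29.10 | 0.366 | 1.3% |
| 0.50 | 1.5 | 17.79 | 0.062 | 0.4% |
| 0.70 | 0.5 | 32.78 | 2.412 | 7.4% |
| 0.70 | 1.0 | 17.51 | 0.457 | 2.6% |
| 0.70 | 1.5 | 6.72 | 0.059 | 0.9% |
| 0.85 | 0.5 | 22.12 | 2.704 | 12.2% |
| 0.85 | 1.0 | 5.77 | 0.266 | 4.6% |
| 0.85 | 1.5 | 0.77 | 0.011 | 1.5% |

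Among results whose baseline was already out of range, about half of the double flags (49% to 50%) were H–D or L–I. With no drug effect, baseline and later value are interchangeable, so this is what one expects.

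To put this on the trial's scale, sections 12.1.1 and 12.1.2 schedule three rounds of tests after dosing begins in Part A (8 h, 24 h, follow-up). Part B has four (24 h after the Day 1 dose, Day 8, outpatient visit, follow-up). That gives 36 × 3 × 33 + 24 × 4 × 33 = 3,564 + 3,168 = 6,732 results. The expected number of H–D or L–I values, active and placebo together, runs from 6,732 × 0.011/1,000 = 0.07 to 6,732 × 2.704/1,000 = 18.2. At d = 1.0 SD it is 1.8 to 3.1.

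**The case against.** PCI means potential importance, and a sensitive, direction-neutral screen is defensible in a first-in-human study. A large post-dose fall in a count that is still high can merit a look. The flags are distinct letters, so a reader of the listings should be able to separate the pairs. The predetermined amounts might be set differently by direction, and section 16.1.1 leaves an SAP to be written before first database lock. All of this stands. It argues for keeping these values in the listings. It does not justify pooling them in the frequency.

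Several stronger readings are tempting but unsupported:

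- **Every out-of-range baseline is at risk.** A reader might take 5% of 1,980, about 100 values. Step 2 shows that a baseline just outside the limit cannot produce H–D or L–I.
- **One such value moves a group's PCI rate by 17 to 25 percentage points.** This takes 1/6 and 1/4 as the steps, but section 16.1.6.2 counts values and states no per-subject denominator.
- **The comparison of active with placebo is biased.** With no drug effect, randomisation gives both arms the same expected rate of these flags.
- **Laboratory safety rests on this table.** The plan also summarises the laboratory data by treatment, adverse events, vital signs and ECGs. Abnormal results become adverse events under the criteria in section 14.2, not through the double flag. The safety review group looks at the laboratory tests themselves (section 8.5.1), and no stopping criterion in sections 8.4 or 9.4.2 refers to PCI.

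**Conclusion.** The point holds and is minor. As worded, the rule counts recovering values as PCI alongside worsening ones, and that part needs no assumption. Its size does. With thresholds of 0.5 to 1.5 SD and the other assumptions above, recovering pairs make up about 0.4% to 12% of double flags, and the upper end needs a low threshold with high within-subject correlation. Exclusion criterion 2, and the use of a pre-dose repeat as baseline where one is taken, should lower the count further. The real figure cannot be fixed without the investigator's amounts. The consequence is a frequency table that is harder to interpret. The documents do not support calling these flags false, or saying that the plan's safety conclusions depend on them.

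**What to change.** In the SAP, before first database lock and unblinding, keep the double-flag definition for the PCI listings so that every such value and its related results stay visible. Tabulate the PCI frequencies by flag pair. Make H with I and L with D the headline PCI count, and show H with D and L with I in separate rows. State whether the table counts values or subjects, and give the denominator.

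The cost is a few lines of SAP text, a small programming change and a slightly longer table. Removing the H–D and L–I pairs from PCI altogether would be simpler, but it would drop large changes from the listing that sets them beside related results.
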